3. STUDY DESIGN

This is a Phase 3, multicenter, international, three-arm, parallel design, placebo-controlled, randomized study with a 30-month double-blind treatment phase, to determine efficacy, safety and tolerability of tafamidis on clinical outcomes in subjects with either transthyretin genetic variants or wild-type transthyretin resulting in amyloid cardiomyopathy (TTR-CM).

There will be approximately 400 subjects enrolled in the study in a 2:1:2 ratio (placebo:20 mg:80 mg). The subjects will be allocated to the 3 arms of the study in the following manner: n=160 in the placebo arm, n=80 in the 20 mg arm, and n=160 in the 80 mg arm. Subjects who experience adverse events that may be associated with poor tolerability to treatment with tafamidis that may impact dosing adherence have the option of blinded treatment re-assignment and potential dose reduction (see [Section 5.5](#)). Subjects will be stratified during enrollment by TTR genotype (variant and wild-type) and structured such that greater than 30% of randomized subjects have a TTR mutation and greater than 30% of subjects have a diagnosis of wild-type TTR cardiomyopathy, with the intent to enroll comparable numbers between the variant and wild-type groups.

Enrollment may be closed for either wild-type or variant stratum in order to enroll at least 30% of subjects with each TTR genotype (wild-type and variant).

Additionally, stratification to treatment assignment will be done for Baseline severity of disease based on NYHA classification (NYHA Class I and NYHA Classes II and III combined). Stratification will be implemented in order to maintain a balance of both TTR genotype and disease severity across the treatment assignments. The site will ensure a Month 30 follow-up contact to determine the subject's vital status and whether the subject has had a heart and / or liver transplant or implantation of cardiac mechanical assist device. Upon completion of the study at the Month 30 visit, subjects may be eligible for -treatment with tafamidis in a separate extension study (B3461045), which will permit the collection of additional safety and efficacy data, and may include the assessment of hospitalizations, mortality, and other outcomes relating to disease progression. For the purpose of this study, 30 months is defined as 910 days. Eligibility for the extension study (B3461045) requires subject participation in this study at least through Day 896 (Month 30 minus 2 weeks).

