9.1. Sample Size Determination

The primary comparison of interest is the pooled tafamidis 20 mg and 80 mg treatment groups vs. placebo. The target sample size is 400 subjects.

A sample size of 400 subjects is based on findings from study Fx1B-201 (a 12-month, open-label study of tafamidis in TTR-CM subjects), TRACS (an observational study with no treatment intervention other than standard of care in TTR-CM subjects), an understanding of current clinical outcomes in this population, and the uncertainty of the assumptions derived from these limited data.

Given that no closed-form sample size estimation solution is available for the primary analysis method, sample size estimation was performed based on simulations.

Sample size assumptions include:

1. All-cause mortality rate of 12.5% for the tafamidis group and 25.0% for the placebo group (ie, a 50% reduction in mortality with treatment).
2. 1.5 cardiovascular-related hospitalizations for the tafamidis group and 2.5 cardiovascular-related hospitalizations for the placebo group.
3. Treatment duration of 30 months.
4. Significance level (alpha) of 0.05 (two-sided test).

With these assumptions, 300 subjects (n=120 for placebo, n=60 for 20 mg, n=120 for 80 mg) yields a power of over 90% for the primary comparison. A more conservative assumption of 30% reduction in mortality (17.5 % for tafamidis and 25% for placebo) yields a power of approximately 80%. With an assumption of 30% reduction in mortality and increasing the number of subjects to 400 subjects (n=160 for placebo, n=80 for 20 mg, and n=160 for 80 mg) yields a power of approximately 90%.

Summary of operating characteristics:

| Assumptions | Sample Size | Power |
|--|--------------------|--------------|
| 50% mortality reduction, hosp frequency 2.5 (pbo), 1.5 (taf) | N=300 | 96% |
| 30% mortality reduction, hosp frequency 2.5 (pbo), 1.5 (taf) | N=300 | 80% |
| 30% mortality reduction, hosp frequency 2.5 (pbo), 1.5 (taf) | N=400 | 90% |

pbo=placebo, taf=tafamidis

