$$E(D_i) = m_k/n_k \text{ and}$$

$$\text{cov}(D_i, D_j) = \frac{m_k(n_k - m_k)}{(n_k - 1)n_k} (\delta_{ij}n_k - 1),$$

where δ_{ij} is the Kronecker delta (valued as 1 if $i=j$ and 0 otherwise).

Since $\sum_{i \in A_k} U_i = \mathbf{0}$ this implies that the mean of T is zero and its variance is

$$V = \sum_k \frac{m_k(n_k - m_k)}{n_k(n_k - 1)} (\sum_{i \in A_k} U_i^2).$$

The hypothesis of interest is tested by comparing T/\sqrt{V} to the normal distribution.

In the event there is insufficient information for the adjudication process to classify either a mortality or hospitalization as cardiovascular related or not cardiovascular related, then the event will be classified as “indeterminate”. In the adjudication process, cases with at least some information indicating a contributory cardiovascular cause, including ambiguous cases, will be adjudicated to the cardiovascular-related category. The test statistic for the “by TTR Genotypes” subgroup analysis will be stratified by NYHA baseline classification (NYHA Classes I and II combined and NYHA Class III). The test statistic for the “by NYHA classifications” subgroup analysis will be stratified by TTR Genotype (variant and wild-type). Subjects who were incorrectly classified during randomization (wrong TTR Genotype or NYHA baseline classification) will be analyzed using the correct TTR Genotype or NYHA baseline classification values.

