8.1.2. Survival Analyses

Time to event endpoints including all-cause mortality, and cardiovascular-related mortality will be analyzed using SAS Proc Lifetest; p-values will be from the log-rank test. For cardiovascular-related mortality, subjects who died for reasons other than cardiovascular (including “indeterminate”) will be designated as censored at the time of death. Subjects who discontinue for transplantation (ie, heart transplantation and combined heart and liver transplantation) or cardiac mechanical assist device will be handled in the same manner as death (as done in the primary analysis).

Kaplan-Meier survival curves for each treatment group along with median survival times (if applicable) will be presented. Kaplan-Meier product limit estimators will be generated. The number of subjects at risk, number of events and number of censored observations through 6, 12, 18, 24, 30 months will be summarized using the “Method=Life” option in PROC LIFETEST.

Time to event endpoints will also be analyzed using Cox proportional hazards model using Proc PHREG with treatment, TTR genotype (variant and wild-type), and NYHA baseline classification (NYHA Classes I and II combined and NYHA Class III) as factors.

For the analyses by NYHA baseline classification, the Cox proportional hazard model will include treatment and TTR genotype. For the analyses by TTR genotype, the model will include treatment and NYHA baseline classification. The Kaplan-Meier survival curves will also be generated for the analyses by NYHA baseline classification and TTR genotype.

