8.1.3. Mixed Model Repeated Measures (MMRM) Analyses

The endpoints evaluated at multiple time points will be analyzed *using a mixed model repeated measures ANCOVA (MMRM) with an unstructured covariance matrix (or as appropriate); center and subject-within-center as random effects; treatment, visit, TTR genotype (variant and wildtype), and visit-by-treatment interaction, as fixed effects and Baseline score as covariate.* While the NYHA baseline classification may serve as an indicator of baseline severity, the endpoints that are evaluated at baseline (and at multiple points post-baseline) will use their respective baseline scores as the appropriate covariate for the MMRM analysis described above.

For the analyses by TTR genotype, the same model specified above will be used, with the addition of terms for TTR genotype-by-treatment interaction and TTR genotype-by-treatment-by-visit 3-way interaction. Similarly for dose, the same model specified above will be used with replacement of “dose” for “treatment”. Appropriate CONTRAST statements will be used to generate the LSMEANS from the MMRM model (eg, for dose, 20 mg vs placebo and 80 mg vs placebo) at each post-baseline study visit. The subgroup analysis by NYHA baseline classification (NYHA Classes I and II combined and NYHA Class III) will be done using ANCOVA (MMRM) with an unstructured covariance matrix (or as appropriate); center and subject-within-center as random effects; treatment, visit, TTR genotype (variant and wildtype), NYHA baseline classification, visit-by-treatment interaction, NYHA baseline classification-by-treatment interaction, NYHA baseline classification-by-treatment-by-visit 3-way interaction as fixed effects and baseline score as covariate. All the subgroup analyses will be considered exploratory.

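### For the primary Finkelstein-Schoenfeld analysis and for mortality, the SAP plans separate within-subgroup analyses by genotype and NYHA class but no comparison between the subgroups

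*SAP*

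**What the plan says.** **Primary analysis.** SAP 8.1.1 describes the FS result by genotype as a separate test within each genotype: the "subgroup analysis will be stratified by NYHA baseline classification". The analysis by NYHA class mirrors this, stratified by genotype. SAP 8.2.4 labels both exploratory.

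**Mortality.** SAP 8.1.2 fits a Cox model within each genotype: "For the analyses by TTR genotype, the model will include treatment and NYHA baseline classification". Within each NYHA class the model has treatment and genotype. Kaplan-Meier curves are drawn by subgroup. The overall Cox model, in the text and in the sample code of Appendix 1.3, has main effects only.

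**Other endpoints.** For the repeated-measures endpoints, SAP 8.1.3 extends the model by genotype "with the addition of terms for TTR genotype-by-treatment interaction and TTR genotype-by-treatment-by-visit 3-way interaction", and does the same for NYHA class. The ANOVA for days in hospital (8.1.4) and the overall Poisson model for hospitalization counts (8.1.5) contain treatment-by-genotype and treatment-by-NYHA terms.

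**Design.** Protocol Section 3 stratifies on genotype, sets a floor of 30% for each genotype "with the intent to enroll comparable numbers between the variant and wild-type groups", and allows one genotype stratum to be closed to reach it.

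Neither document says how consistency across genotype or NYHA class will be judged.

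**The concern.** The enrollment floor makes results by genotype something readers will look at. The earlier evidence by genotype is thin: Protocol 1.2.1 reports that only 4 of the 35 subjects in the open-label study carried V122I. On the two endpoints that matter most, the plan will give an estimate and a p-value for each genotype but no estimate of how far the two differ.

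Two separate p-values are a poor substitute for that estimate. Splitting the sample lowers power in each part, so one genotype can miss 0.05 when the true effect is the same in both. At stake is the description of the result by genotype and NYHA class, not the primary test.

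**Working it through.** **Inputs (Protocol 9.1 unless noted).** Two-sided alpha is 0.05. There are 160 placebo and 240 pooled tafamidis subjects. FS power is 90% at N=400 under a 30% mortality reduction (17.5% against 25%), 80% at N=300 for the same effect, and 96% at N=300 under a 50% reduction: "All-cause mortality rate of 12.5% for the tafamidis group and 25.0% for the placebo group". Hospitalization assumptions are "1.5 cardiovascular-related hospitalizations for the tafamidis group and 2.5 cardiovascular-related hospitalizations for the placebo group", with no dispersion given. The genotype split runs from 50/50 (intended) to 30/70 (the floor), from Protocol Section 3.

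**Reproducing the plan's power.** The stratified FS test was simulated with the SAP's formulas for T and V (2,000 trials per setting). Pure Poisson counts give 100%, 99.5% and 99.9% against the stated 96%, 80% and 90%. Negative-binomial counts with dispersion 1.0 give 94.8%, 81.9% and 90.8%; with 1.1 they give 94.6%, 79.1% and 89.9%. The stated figures are therefore reproducible within 2 points, but the dispersion is an assumption.

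**Formulas.** With the same true effect in both genotypes and overall expected z:
- power in a genotype with share s is Φ(z√s − 1.96), plus a negligible opposite tail;
- with powers a and b, the chance that exactly one reaches 0.05 is a(1−b) + b(1−a).

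**Primary, 90% power.** z = 1.96 + 1.2816 = 3.24.
- 50/50: power is Φ(2.292 − 1.96) = 63% in each genotype. Exactly one: 2 × 0.63 × 0.37 = 46.6%.
- 30/70: powers are Φ(1.776 − 1.96) = 42.7% and Φ(2.712 − 1.96) = 77.4%. Exactly one: 0.427 × 0.226 + 0.774 × 0.573 = 54.0%.

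Simulating the FS test itself (dispersion 1.1) gives 47.9% and 55.0%. Given a significant overall result, the normal approximation gives about 49% and 58%.

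**Primary, 50% reduction.** z = (1.96 + 1.7507) × √(400/300) = 4.28.

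**All-cause mortality.** z = √(events × 0.4 × 0.6) × |ln HR|.
- 30% reduction: 160 × 0.25 + 240 × 0.175 = 82 events. HR = ln(0.825)/ln(0.75) = 0.669, so z = 1.79 and overall power is 43%.
- 50% reduction: 40 + 30 = 70 events. HR = ln(0.875)/ln(0.75) = 0.464, so z = 3.15 and overall power is 88%.

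| Analysis at N=400 | Exactly one p<0.05, 50/50 | Exactly one p<0.05, 30/70 | Opposite directions |
|---|---|---|---|
| Primary, 30% reduction (90% power) | 46.6% | 54.0% | 2.2% to 4.1% |
| Primary, 50% reduction | 24.4% | 36.5% | 0.2% to 1.0% |
| Mortality, 30% reduction | 36.8% | 38.0% | 18.5% to 21.0% |
| Mortality, 50% reduction | 47.8% | 54.7% | 2.6% to 4.6% |

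For the primary under the 50% reduction, simulation gives 29.5% and 38.9%. For mortality under the 30% reduction, neither genotype reaches 0.05 in about 57% of trials.

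**NYHA class.** The documents do not state the split for this trial. If Class III were 25% or 10% of subjects (an assumption), the primary at 90% power would give 58% or 74%.

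**What a direct comparison would do.** With identical effects, a 5% heterogeneity test signals a difference in 5% of trials. A simulation of such a test on the FS net win (4,000 trials per setting, assumed dispersion 1.05 and 25% Class III) gave 5.1%, 4.0% and 4.7% at 30/70, 40/60 and 50/50. If the full effect sat in one genotype and none in the other, its power would be Φ(3.24 × √(s(1−s)) − 1.96), which is 37% at 50/50 and 32% at 30/70. For mortality, holding events at the design count, it would be 15% and 13% at HR 0.669 against 1, and 35% and 30% at HR 0.464 against 1.

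**The case against.** The strongest reply is that the plan never says consistency will be judged by comparing p-values. The subgroup analyses are labelled exploratory, and SAP 8.2.2 confines formal inference to the primary, then 6MWT, then KCCQ. The Cox fits and Kaplan-Meier curves give estimates as well as p-values. Protocol Section 3 gives balance across treatment assignments as the reason for stratifying, and no objective or hypothesis concerns genotype consistency. All of this stands. A reader might infer that the plan uses within-subgroup significance as its consistency criterion; the documents support only the statement that it has no criterion.

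A second reply is that FS and mortality were not singled out. The Poisson analyses by genotype and by NYHA class (SAP 8.1.5) are also separate fits, as are the TTR stabilization tests (8.1.6). For the repeated-measures models, SAP 8.1.3 mentions contrasts to obtain adjusted means and promises no interaction p-value. This also stands and narrows the contrast. The difference that remains is that those repeated-measures models, the ANOVA and the overall Poisson model contain the terms from which a between-subgroup comparison can be taken, while nothing planned for FS or mortality does.

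A third reply is that an interaction test would often miss a real difference. With power of 32% to 37% (primary) or 13% to 35% (mortality) even when one genotype has no effect, reading a non-significant result as consistency would mislead in 63% to 87% of such trials. This is right, and it shapes the remedy.

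**Conclusion.** The gap is real and modest. For the primary analysis and mortality the SAP plans no between-subgroup estimate, and adding one is a cheap improvement. If separate p-values were compared, genotypes with the same effect would land on opposite sides of 0.05 in about 47% to 54% of trials for the primary at 90% power, and in roughly 25% to 55% across the plan's scenarios.

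Three stronger readings are not supported. Discordance in about half of trials is not general: it holds for the primary at 90% power and for mortality under the 50% reduction, but not for the primary under the 50% reduction or for mortality under the 30% reduction. Discordance refers only to the 0.05 threshold; it does not mean that the genotypes would appear to respond in opposite directions. Nothing here affects the primary conclusion or its type I error.

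The figures assume z proportional to the square root of the sample size, independent genotypes, equal event rates in both and a split between 50/50 and 30/70. The FS simulations also rest on the assumed dispersion.

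**What to change.** **SAP 8.1.1.** For genotype and for NYHA class, add the between-subgroup difference in net win, where the net win in subgroup g is θ_g = T_g / Σ_k m_k(n_k − m_k), summed over its strata. Treated-against-treated scores cancel in T, so θ_g is wins minus losses per treated-placebo pair. Report the difference with a 95% CI and a one-degree-of-freedom heterogeneity test. Use a U-statistic or bootstrap variance for the CI, because the SAP's V is a permutation variance under the null hypothesis. The subgroups occupy separate strata, so their estimates are independent.

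**SAP 8.1.2.** Add a separate exploratory Cox model with treatment-by-genotype and treatment-by-NYHA terms, and report each ratio of hazard ratios with its 95% CI. Leave the overall main-effects model as it is.

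**Both sections.** State that consistency is described from these estimates and intervals, not from within-subgroup significance and not from a non-significant interaction p-value alone. State that power is low and the results are exploratory.

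**Cost.** A few sentences of SAP text and a little programming, with no new data. The intervals will be wide, and saying so in advance is part of the benefit.

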8.1.3. Mixed Model Repeated Measures (MMRM) Analyses

The endpoints evaluated at multiple time points will be analyzed *using a mixed model repeated measures ANCOVA (MMRM) with an unstructured covariance matrix (or as appropriate); center and subject-within-center as random effects; treatment, visit, TTR genotype (variant and wildtype), and visit-by-treatment interaction, as fixed effects and Baseline score as covariate.* While the NYHA baseline classification may serve as an indicator of baseline severity, the endpoints that are evaluated at baseline (and at multiple points post-baseline) will use their respective baseline scores as the appropriate covariate for the MMRM analysis described above.

For the analyses by TTR genotype, the same model specified above will be used, with the addition of terms for TTR genotype-by-treatment interaction and TTR genotype-by-treatment-by-visit 3-way interaction. Similarly for dose, the same model specified above will be used with replacement of “dose” for “treatment”. Appropriate CONTRAST statements will be used to generate the LSMEANS from the MMRM model (eg, for dose, 20 mg vs placebo and 80 mg vs placebo) at each post-baseline study visit. The subgroup analysis by NYHA baseline classification (NYHA Classes I and II combined and NYHA Class III) will be done using ANCOVA (MMRM) with an unstructured covariance matrix (or as appropriate); center and subject-within-center as random effects; treatment, visit, TTR genotype (variant and wildtype), NYHA baseline classification, visit-by-treatment interaction, NYHA baseline classification-by-treatment interaction, NYHA baseline classification-by-treatment-by-visit 3-way interaction as fixed effects and baseline score as covariate. All the subgroup analyses will be considered exploratory.

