9.2.2. Analysis of Key Secondary Endpoints

The key secondary endpoints will be evaluated using a mixed model repeated measures ANCOVA with an unstructured covariance matrix (or as appropriate); center and subject-within-center as random effects; treatment, visit, TTR genotype (variant and wild-type), and visit-by-treatment interaction, as fixed effects and Baseline score as covariate.

The key secondary variables are:

1. Change from Baseline to Month 30 in distance walked during the 6MWT ([Appendix 4](#)).
2. Change from Baseline to Month 30 in KCCQ ([Appendix 1.1](#)) Overall Summary score.

To maintain the type 1 error rate at or below the specified level, a pre-specified hierarchical order for testing as indicated above will be used to maintain the overall alpha at 0.05 for these two key secondary endpoints. The multiplicity procedure will be applied to the ITT analysis set only.

Supplemental analyses of the two key secondary variables will be performed to support the robustness of the conclusions drawn. The pattern-mixture analysis will group the subjects on the basis of their dropout or missing-data patterns. A grouping variable for this analysis is defined in the SAP.

Exploratory analyses of the key secondary endpoints will include results from the MMRM analysis at each individual time point other than Month 30.

Additional exploratory analyses of the key secondary endpoints will include results from the MMRM analysis at each individual time point by dose group (randomized dose group), TTR genotype (variant and wild-type), and NYHA Baseline classification. Descriptive statistics overall, by dose, by TTR genotype, and by NYHA Baseline classification will be provided for each time point.

Except for the analyses by dose, all analyses of the key secondary endpoints, including the proposed exploratory analyses of these endpoints, will compare the pooled tafamidis group with the placebo group.

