Table 2 Summary of Proposed Efficacy and Safety Analyses	Updated to reflect the changes to SAP.	Table updated to be consistent with the body of SAP and protocol amendment 1.
Appendix 1.2. Sample SAS Code for Analyses	
 Added code for pattern-mixture. Made a minor correction to the SAS code for analyses described in Section 8.1.3, ie, added RANDOM statement. 	
 Added SAS code for new pattern-mixture analysis consistent with May 2014 agreement with FDA. Made minor correction to previous SAS code.

Amendment 2 (SAP Version 3)

Section of the SAP	Summary of change	Rationale
Sections 2.1, 8.1.1, 8.1.2, 8.2.4	Cardiac mechanical assist device was added as a reason for discontinuation and treated similar to heart transplant in the analysis.	Cardiac mechanical assist device is indicative of end stage disease similar to a heart transplant.
Section 8.2.5	Removed specification of an unnecessary table.	Listing of adverse events occurring during the trial will include those that start prior to randomization.

Amendment 3 (SAP Version 4)

Section of the SAP	Summary of change	Rationale
Sections 6.4, 8.1.1, 8.1.2, 8.1.3, 8.1.4, 8.1.5, 8.1.6, 8.2.4	NYHA baseline classification categories were change from “NYHA class I and NYHA classes II and III combined ” to “NYHA classes I and II combined and NYHA class III”.	
Redefined the baseline groupings for New York Heart Association (NYHA) Functional Classification that will be used for efficacy analyses, grouping subjects with NYHA Class I and II together to be compared against NYHA Class III.
 
Given the very low number of enrolled subjects with NYHA Class I, the NYHA baseline groupings were redefined for efficacy analyses. This permits a more appropriate baseline adjustment in the primary analysis as well as other secondary and exploratory analyses.

Section 2.1	Study number of the extension study included and other edits.	Edits to reflect the changes to the protocol.
Section 6.1.4, Section 8.2.4, Table 2	KCCQ subjects symptoms subscales clarified.	Better delineated the analysis planned for Kansas City Cardiomyopathy Questionnaire (KCCQ) scores related to subject symptoms.
Section 6.2	Text updated to be consistent with protocol.	The italicized text was update to be consistent with protocol.

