2.1. Study Design

This is a Phase 3, multicenter, international, three-arm, parallel design, placebo-controlled, randomized study with a 30-month double-blind treatment phase, to determine efficacy, safety and tolerability of tafamidis on clinical outcomes in subjects with either transthyretin genetic variants or wild-type transthyretin resulting in amyloid cardiomyopathy (TTR-CM).

There will be approximately 400 subjects enrolled in the study in a 2:1:2 ratio (placebo:20 mg:80 mg). The subjects will be allocated to the 3 arms of the study in the following manner: n=160 in the placebo arm, n=80 in the 20 mg arm, and n=160 in the 80 mg arm. Subjects who experience adverse events that may be associated with poor tolerability to treatment with tafamidis that may impact dosing adherence have the option of blinded treatment re-assignment and potential dose-reduction (see [Section 5.5 of protocol](#)). Subjects will be stratified during enrollment by TTR genotype (variant and wild-type) and structured such that greater than 30% of randomized subjects have a TTR mutation and greater than 30% of subjects have a diagnosis of wild-type TTR cardiomyopathy, with the intent to enroll comparable numbers between the variant and wild-type groups.

Enrollment may be closed for either wild-type or variant stratum in order to enroll at least 30% of subjects with each TTR genotype (wild-type and variant).

Additionally, stratification to treatment assignment will be done for Baseline severity of disease based on NYHA classification (NYHA Class I and NYHA Classes II and III combined). Stratification will be implemented in order to maintain a balance of both TTR genotype and disease severity across the treatment assignments. The site will ensure a Month 30 follow-up contact to determine the subject's vital status and whether the subject has had a heart and / or liver transplant or implantation of cardiac mechanical assist device. Upon completion of the study at the Month 30 visit, subjects may be eligible for treatment with tafamidis in a separate study (B3461045), which will permit the collection of additional safety and efficacy data, and may include the assessment of hospitalizations, mortality, and other outcomes relating to disease progression. For the purpose of this study, 30 months is defined as 910 days. Eligibility for the extension study (B3461045) requires subject participation in this study at least through Day 896 (Month 30 minus 2 weeks).

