6.4. Covariates

Baseline values will be included as a covariate in the analysis using the mixed model repeated measures (MMRM) model detailed in [Section 8.1.3](#). Where baseline scores are not available (or applicable) for the endpoints (eg, frequency of cardiovascular-related hospitalization), the NYHA baseline classification (NYHA Classes I and II combined and NYHA Class III) will be included in the appropriate models to address baseline severity levels.

All subjects who were incorrectly classified during randomization (wrong TTR Genotype or NYHA baseline classification) will be analyzed using the correct TTR Genotype or NYHA baseline classification values.

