Appendix 1.3. Sample SAS Code for Analyses Described in Sections 8.1.2 – 8.2.6

Sample SAS code to fit the mixed model repeated measures specified in [Section 8.1.3](#) is given below. The response variable Y is the change from baseline at the study visits.

```
PROC MIXED DATA=xxx METHOD=REML EMPIRICAL;  
CLASS pid center trt visit genotype;  
MODEL y= ybase trt visit genotype trt *visit;  
RANDOM int/SUBJECT=center;  
  
REPEATED visit /SUBJECT= pid (center) r type=UN;  
  
RUN;
```

Sample SAS code for the survival analysis specified in [Section 8.1.2](#) is given below.

```
PROC LIFETEST DATA=xxx PLOTS=(s) graphics;  
TIME dur *status(0);  
STRATA trt;  
RUN;  
  
PROC PHREG DATA=xxx;  
MODEL dur*status(0)=trt genotype NYHAbase/ ties=EXACT;  
RUN
```

Sample SAS code for the ANOVA specified in [Section 8.1.4](#) is given below.

```
PROC GLM DATA=xxx;  
CLASS trt genotype NYHAbase;  
MODEL y= trt genotype NYHAbase trt*genotype trt*NYHAbase;  
RUN;
```

Sample SAS code for the Poisson regression specified in [Section 8.1.5](#) is given below.

```
PROC DATA=xxx;  
ln_styyr=log(styyr);* log transformation to normalize duration of participation ;  
RUN;  
  
PROC GENMOD DATA=xxx;  
CLASS trt genotype NYHAbase;  
MODEL y= trt genotype NYHAbase trt*genotype  
trt*NYHAbase/ type 3 dist=poisson link=log offset=ln_styyr;  
RUN;
```

Sample SAS code for the CMH test specified in [Section 8.1.6](#) is given below. In the code below, the variable NYHA_GENOTYPE is obtained from combining NYHA baseline classification and TTR genotype into one variable (with 4 levels).

```
PROC FREQ DATA=xx;
TABLES NYHA_GENOTYPE*TRT*STABILIZED / CMH
RUN;
```

Sample SAS code for the pattern mixture analysis specified in [Section 8.1.5](#) is given below.

```
PROC MIXED DATA=xxx empirical;
CLASS pid visit center trt pattern genotype;
MODEL y= ybase visit trt genotype pattern visit*trt
trt*pattern / solution;
random int/subject=center;
repeated visit /subject= pid (center) r type=UN;
ESTIMATE 'Tafamidis vs placebo Month 30'
trt 1 -1 visit*trt 0 0 0 0 0 0 0 1 -1
trt*pattern 0.5 0.5 -0.5 -0.5 /cl e; * Placebo adjusted LSMEANS of Tafamidis
averaged over the pattern (equal weight=0.5);
run;
```

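### Adding NYHA class and a baseline-by-visit term to the 6MWT and KCCQ-OS model would be a nearly free gain in precision and robustness, of unknown and probably small size

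*SAP*

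**What the plan says.** Protocol 9.2.2 gives the model for 6MWT and KCCQ-OS as "treatment, visit, TTR genotype (variant and wild-type), and visit-by-treatment interaction, as fixed effects and Baseline score as covariate", with centre and subject within centre as random effects. SAP 8.1.3 repeats it, ending "and visit-by-treatment interaction, as fixed effects and Baseline score as covariate". The PROC MIXED code in SAP Appendix 1.3 matches: "MODEL y= ybase trt visit genotype trt *visit". None of the three contains NYHA class or a baseline-by-visit term.

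The NYHA omission follows a stated rule. SAP 6.4 brings NYHA in "Where baseline scores are not available (or applicable) for the endpoints", and SAP 8.1.3 adds: "While the NYHA baseline classification may serve as an indicator of baseline severity", endpoints with their own baseline measurement "will use their respective baseline scores as the appropriate covariate for the MMRM analysis described above". No reason is given for holding the baseline slope constant from Month 6 to Month 30.

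Elsewhere, NYHA I and II versus III is used in the Finkelstein-Schoenfeld strata (SAP 8.1.1) and in the Cox, ANOVA, Poisson and CMH analyses (SAP 8.1.2, 8.1.4 to 8.1.6). MMRM data are not imputed (SAP 7). The supplemental pattern-mixture model (SAP 8.2.2) adds pattern and treatment-by-pattern, but neither of the two terms discussed here.

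**The concern.** After the primary analysis, 6MWT and KCCQ-OS are the only endpoints under type I error control, and they are tested in sequence: if 6MWT misses 0.05, KCCQ-OS cannot be declared significant (SAP 8.2.2). Precision lost on 6MWT therefore affects both.

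Two mechanisms are possible. First, NYHA class may predict the rate of decline beyond what the baseline score tells, and the relation between baseline and change may shift over 30 months; a model without these terms leaves explainable variance in the residual. Second, the MMRM relies on data being missing at random given the model and the observed scores. If NYHA class predicts who dies or drops out, and does so differently by arm, leaving it out weakens that assumption.

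The SAP's rule treats baseline score and NYHA class as substitutes, but its own choices do not require that. The exploratory NYHA-subgroup MMRM in SAP 8.1.3 contains both. The imputation model for the primary analysis (SAP Appendix 1.4) keeps NYHA class even when a subject's earlier hospitalisation counts are in the model.

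**Working it through.** **No plan figure to reproduce.** The power figures in Protocol 9.1 (96%, 80%, 90%) concern the primary test. No SD, effect size, dropout or power is given for 6MWT or KCCQ-OS, so what follows rests on assumptions, shown as ranges.

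**Inputs from the documents.** 160 placebo versus 240 pooled tafamidis; visits at Months 6, 12, 18, 24 and 30; two-sided alpha 0.05; NYHA III or higher in 24.1% (7/29) of the observational study and 5.7% (2/35) of the open-label study (Protocol 1.2.1).

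**Closed form, NYHA only.** With prevalence p of NYHA III and a gap of g SD between classes given the baseline score, partial R² = p(1−p)g² / (1 + p(1−p)g²), and the SE ratio is √(1 − R²). For p = 0.241 and g = 0.5: p(1−p)g² = 0.0457, R² = 0.0437, ratio 0.978. Full range:

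| p | g = 0.25 | g = 0.5 | g = 1.0 |
|---|---|---|---|
| 5.7% | 0.998 | 0.993 | 0.974 |
| 24.1% | 0.994 | 0.978 | 0.919 |
| 30% (assumed) | 0.994 | 0.975 | 0.909 |

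**Simulation, both terms.** Unstructured MMRM fitted by maximum likelihood, sandwich standard errors as the EMPIRICAL option implies, no centre effect, 700 replicates, true Month 30 difference 0.30 SD. Ratios compare the SAP model plus NYHA-by-visit and baseline-by-visit with the SAP model. Bias is that of the SAP model, in SD units, with Monte Carlo error 0.005.

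| Scenario | Missing at Month 30 | Mean SE ratio | Empirical SD ratio | Bias |
|---|---|---|---|---|
| A: NYHA gap 0.25 SD, constant slope, equal dropout | 37% | 0.997 | 1.004 | 0.007 |
| B: gap 0.5 SD, slope varies, NYHA-related dropout equal by arm | 41% | 0.968 | 0.995 | 0.005 |
| C: as B, NYHA-related dropout greater on placebo | 35% | 0.977 | 0.976 | −0.021 |
| D: 5.7% NYHA III | 36% | 0.975 | 0.966 | −0.004 |
| E: gap 1 SD, strong slope change, NYHA-related dropout greater on placebo | 36% | 0.894 | 0.885 | −0.042 |

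**Precision into power.** New power = Φ((1.960 + z)/k − 1.960), where k is the SE ratio and z the normal quantile of the starting power. From 80% (z = 0.842): k = 0.997 gives 80.2%; k = 0.97 gives 2.802/0.97 − 1.960 = 0.928, or 82.3%; k = 0.90 gives 87.6%. In sample size, 1 − 0.968² = 6% and 1 − 0.894² = 20%.

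**Which term removes the bias.** Against the true 0.30 SD, the bias in C and E is 0.021/0.30 = 7% and 0.042/0.30 = 14%, towards no effect. Adding NYHA-by-visit alone brought it to 0.003 in both. Adding baseline-by-visit alone did not help (−0.036 and −0.071). With both terms it was 0.004 and 0.006.

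**The case against.** The strongest reply is that the plan follows a coherent rule. Mortality, hospitalisation counts and days in hospital have no baseline score, so adjusting them for NYHA while giving 6MWT and KCCQ-OS their own baseline is no inconsistency. That stands. The MMRM also uses each subject's earlier post-baseline scores, which carry part of the NYHA information, and the SAP already plans two pattern-mixture analyses and an exploratory NYHA-subgroup MMRM. None of these gives an overall NYHA-adjusted treatment difference with a visit-specific baseline slope, so the suggestion survives, but as an improvement only.

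A reader might infer three stronger things that the documents do not support.

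- *That a stratification factor is ignored and inference suffers.* Randomisation was stratified "based on NYHA classification (NYHA Class I and NYHA Classes II and III combined"), whereas the analyses contrast I and II with III. The SAP regrouped "Given the very low number of enrolled subjects with NYHA Class I", so the actual stratification factor separates few subjects. The case rests on prognosis and dropout, not on stratification.
- *That 4 to 6 power points are being lost.* A smaller simulation (250 trials per scenario, 30% NYHA III assumed) showed power rising from 84% to 90% in one scenario and from 87% to 90% in another. Its standard errors fell from 0.0758 to 0.0729 and from 0.0742 to 0.0715, ratios of 0.962 and 0.964. By the formula above these imply 83.6% to 86.3% and 86.8% to 89.1%, or 2 to 3 points; the rest is within Monte Carlo error of about 2 points per estimate. The 30% also exceeds both shares in Protocol 1.2.1.
- *That both omissions undermine missing at random.* Baseline score is already in the model. Only NYHA mattered for bias, and only when NYHA-related dropout differed by arm.

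**Conclusion.** Both terms are absent, and the SAP's rule gives no reason against using NYHA class and baseline score together. The plan is not wrong, and no type I error problem is shown.

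The size of the gain is unknown. Under the moderate assumptions it is about 0 to 3% of the Month 30 standard error, worth at most 2 to 3 power points. It reaches about 11% only with a 1 SD NYHA gap and a large change in baseline slope. The robustness gain is conditional: bias of about 0.02 to 0.04 SD arose when NYHA-related dropout was greater on placebo, and none was detectable in the three scenarios where it was equal. The direction of that bias is a feature of those scenarios, not a general result. Differential dropout is plausible, since Protocol 9.1 assumes 25% mortality on placebo against 12.5% on tafamidis, but nothing in the documents says how it relates to NYHA class.

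Confidence is high that the terms are missing and that adding them does no material harm (worst empirical SD ratio 1.004). It is low on how much they would help.

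**What to change.** Before unblinding:

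- In SAP 8.1.3 and Protocol 9.2.2, add NYHA baseline class (I and II vs III), NYHA-by-visit and baseline-by-visit to the fixed effects for 6MWT and KCCQ-OS, and amend the rule in SAP 6.4 to match.
- In SAP Appendix 1.3, add NYHAbase to CLASS and use `MODEL y = ybase ybase*visit trt visit genotype NYHAbase NYHAbase*visit trt*visit;`.
- Make the same change in the pattern-mixture model (SAP 8.2.2 and its code).
- Say whether the change extends to the exploratory endpoints that share SAP 8.1.3.

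If the primary specification is to stay as it is, name this model as a prespecified sensitivity analysis. Do not add baseline-by-visit alone: in the scenarios with differential dropout it left the bias larger.

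The added terms do not interact with treatment, so the quantity estimated remains one treatment difference at Month 30. The cost is a few degrees of freedom and a short text and code edit in several places. The SAP records the study as still blinded, and Protocol Section 9 allows the SAP to modify analyses of this kind.
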